1.4.5.1 Summary of Safety

In CA209001 (n = 39), in which subjects received a single dose of nivolumab (BMS-936558) with possible retreatment at 3 months, the most frequent AEs were fatigue (56%), nausea (44%), proteinuria (38%), constipation (33%), back pain (33%), dry mouth (28%), vomiting (28%), rash (26%), and dyspnea (26%). There was no clear or consistent relationship between the incidence or severity of AEs and the nivolumab (BMS-936558) dose level (0.3, 1, 3, or 10 mg/kg IV single dose, with possible retreatment at 3 months). Of 39 (100%) subjects who had at least one AE, 32 (82%) had Grade 3 or 4 AEs regardless of causality. Three treatment-related SAEs were reported: hypothyroidism (Grade 2), colitis (Grade 3), and anemia (Grade 2). Among 12 deaths, none were considered drug-related.

In CA209003 (n = 296), as of the database lock date of 24-Feb-2012, BMS-936558-related AEs of any grade occurred in 70% of subjects.⁴² The most frequent drug-related AEs occurring in $\geq 5\%$ of subjects included fatigue (24%), rash (12%), diarrhea (11%), pruritus (10%), nausea (8%), decreased appetite (8%), hemoglobin decreased (6%) and pyrexia (5%). The majority of events were low grade, with Grade 3/4 drug-related AEs observed in 14% of subjects. The most common Grade 3/4 drug-related AEs occurring in $\geq 1\%$ of subjects were fatigue (2%), pneumonitis (1%), hypoxia (1%), diarrhea (1%), colitis (1%), abdominal pain (1%), AST/ALT increased (1% each), blood alkaline phosphatase increased (1%), lipase increased (1%), pneumonia (1%), hypophosphatemia (1%), and lymphopenia (1%). Drug-related serious AEs (SAEs) occurred in 11% of subjects. Grade 3/4 drug-related SAEs occurring in $\geq 1\%$ of subjects were: pneumonitis (1%), pneumonia (1%), lipase increased (1%), and diarrhea (1%). The spectrum, frequency, and severity of BMS-936558-related AEs were generally similar across dose levels and histological subtypes. Other drug-related AEs included vitiligo, hepatitis, hypophysitis, and thyroiditis.

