4.3.1 Dose Delay Criteria

4.3.1.1 Nivolumab Dose Delay Criteria

Nivolumab administration should be delayed for the following:

- Any Grade ≥ 2 non-skin, drug-related adverse event, with the following exceptions:
 - Grade 2 drug-related fatigue or laboratory abnormalities do not require treatment delay
- Any Grade 3 skin, drug-related adverse event
- Any Grade 3 drug-related laboratory abnormality, with the following exceptions for lymphopenia, leukopenia, AST, ALT, or total bilirubin:
 - Grade 3 lymphopenia or leukopenia does not require dose delay
 - If a subject has a baseline AST, ALT or total bilirubin that is within normal limits, delay dosing for drug-related Grade ≥ 2 toxicity
 - If a subject has baseline AST, ALT, or total bilirubin within the Grade 1 toxicity range, delay dosing for drug-related Grade ≥ 3 toxicity
- Any adverse event, laboratory abnormality, or intercurrent illness which, in the judgment of the investigator, warrants delaying the dose of study medication.

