4.3.4 Discontinuation Criteria

4.3.4.1 Discontinuation Criteria for Nivolumab

Nivolumab administration should be discontinued for the following:

- Any Grade ≥ 2 drug-related uveitis, eye pain, or blurred vision that does not respond to topical therapy and does not improve to Grade 1 severity within the re-treatment period OR requires systemic treatment
- Any Grade 3 non-skin, drug-related adverse event lasting > 7 days, with the following exceptions for laboratory abnormalities, drug-related bronchospasm, hypersensitivity reactions, and infusion reactions:
 - Grade 3 drug-related laboratory abnormalities do not require treatment discontinuation except:
 - ◆ Grade 3 drug-related thrombocytopenia > 7 days or associated with bleeding requires discontinuation
 - ◆ Any drug-related liver function test (LFT) abnormality that meets the following criteria require discontinuation:
 - AST or ALT > 5 - 10 x ULN for > 2 weeks
 - AST or ALT > 10 x ULN
 - Total bilirubin > 5 x ULN
 - Concurrent AST or ALT > 3 x ULN and total bilirubin > 2 x ULN
 - Grade 3 drug-related bronchospasm, hypersensitivity reaction, infusion reaction, uveitis or pneumonitis of any duration requires discontinuation
- Any Grade 4 drug-related adverse event or laboratory abnormality, except for the following events which do not require discontinuation:
 - Grade 4 neutropenia ≤ 7 days
 - Grade 4 lymphopenia or leukopenia
 - Isolated Grade 4 electrolyte imbalances/abnormalities that are not associated with clinical sequelae and are corrected with supplementation/appropriate management within 72 hours of their onset
- Any dosing interruption lasting > 6 weeks with the following exceptions:
 - Dosing interruptions to allow for prolonged steroid tapers to manage drug-related adverse events are allowed. Prior to re-initiating treatment in a subject with a dosing interruption lasting > 6 weeks, the BMS medical monitor or study director must be consulted. Tumor assessments should continue as per protocol even if dosing is interrupted.
 - Dosing interruptions > 6 weeks that occur for non-drug-related reasons may be allowed if approved by the BMS medical monitor or study director. Prior to re-initiating treatment in a subject with a dosing interruption lasting > 6 weeks, the BMS medical monitor or study director must be consulted. Tumor assessments should continue as per protocol even if dosing is interrupted.

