4.3.4.2 Discontinuation Criteria for Everolimus

As per the approved product label for everolimus, treatment should be continued as long as clinical benefit is observed or until unacceptable toxicity occurs.

For this protocol, subjects must permanently discontinue everolimus for:

- Any drug-related Grade 4 adverse event or laboratory abnormality, except for the following events which do not require discontinuation:
 - Grade 4 neutropenia \leq 7 days
 - Grade 4 lymphopenia or leukopenia
 - Isolated Grade 4 electrolyte imbalances/abnormalities that are not associated with clinical sequelae and are corrected with supplementation/appropriate management within 72 hours of their onset
- Any dosing interruption lasting $>$ 6 weeks with the following exceptions:
 - Dosing interruptions to allow for prolonged steroid tapers to manage drug-related adverse events are allowed. Prior to re-initiating treatment in a subject with a dosing interruption lasting $>$ 6 weeks, the BMS medical monitor or study director must be consulted. Tumor assessments should continue as per protocol even if dosing is interrupted.
 - Dosing interruptions $>$ 6 weeks that occur for non-drug-related reasons may be allowed if approved by the BMS medical monitor or study director. Prior to re-initiating treatment in a subject with a dosing interruption lasting $>$ 6 weeks, the BMS medical monitor or study director must be consulted. Tumor assessments should continue as per protocol even if dosing is interrupted.
- Any adverse event, laboratory abnormality, or intercurrent illness which, in the judgment of the Investigator, presents a substantial clinical risk to the subject with continued everolimus dosing.

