5 STUDY ASSESSMENTS AND PROCEDURES

5.1 Flow Chart/Time and Events Schedule

Table 5.1-1: Screening Procedural Outline (CA209025)			
Procedure	Screening^a	Day -3 to +1 (Post Randomization)	Notes
Eligibility Assessments			
Informed Consent	X		Obtain consent prior to performing any testing for eligibility.
Inclusion/Exclusion Criteria	X	X	All inclusion/exclusion criteria should be assessed prior to randomization
Medical History	X		Include assessment of Pulmonary Risk Factors
Tumor tissue samples	X		May be archival. 1 paraffin block or a minimum of 10 FFPE unstained slides received by Central Lab prior to subject randomization. (FNA and bone metastases samples not acceptable)
Tumor Assessments	X		CT or MRI within 30 days prior to first dose of study drug. Baseline imaging of chest, abdomen, pelvis, brain, and all known sites of disease is required.
Safety Assessments			
Physical Examination	X		Within 30 days of randomization
Vital Signs (including Performance status)	X	X	Screening visit should include weight, height and KPS. Complete vitals should be performed within 3 days prior to first dose of study drug to include: body weight, BP, HR, temperature, and oxygen saturation by pulse oximetry at rest and after exertion (Section 5.3)
Concomitant Medication Collection	X		Within 14 days prior to randomization
Assessment of Signs and Symptoms	X		Within 14 days prior to randomization
Urinalysis	X		Within 14 days prior to randomization to include: protein

Table 5.1-1: Screening Procedural Outline (CA209025)			
Procedure	Screening^a	Day -3 to +1 (Post Randomization)	Notes
Laboratory Tests	X		Local Labs: Within 14 days prior to randomization to include: CBC w/ differential, LFTs (AST, ALT, total bili, alk phosphatase), BUN or serum urea, creatinine, Ca, Mg, Na, K, Cl, albumin, endocrine panel (TSH, free T3, free T4), fasting serum lipids profile including total cholesterol, triglycerides, LDL, and HDL; fasting glucose and Hep B and C testing (HBV sAg, HCV Ab or HCV RNA).
Pregnancy Test	X	X	For WOCBP at screening and within 24 hours of the first dose of study drug (serum or urine) Local/site.
Exploratory Samples		X	Must be obtained prior to dosing. See Table 5.1-6
PGx sample (Optional)		X	Can be obtained at any time after PGx consent is signed
Clinical Drug Supplies			
Randomize		X	First dose of study medication must be administered within 3 working days of randomization.
Other			

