Patient-Reported Outcome Measurements		X	After randomization and prior to first dose: FKSI-DRS and EQ-5D (Use Cycle 1 visit on ePRO tablet for this visit)

^a All testing listed to be performed within 30 days prior to randomization, unless otherwise specified
Note: Screening period is not limited to 30 days, provided testing is performed within time frames noted.

Table 5.1-2: On-Study Procedural Outline Arm A- Nivolumab (BMS-936558)				
Procedure	Each Cycle Day 1	2nd Dose of Cycle	Q 8 wks from Randomization	Notes
Safety Assessments				
Targeted assessments	X			Except Cycle 1. Assessments within 48 hrs of dosing to include: Targeted physical exam, performance status and weight. Oxygen saturation by pulse oximetry at rest and after exertion (Section 5.3).
Adverse Events Assessment	X	X		eSAEs should be approved in TAO by Investigator within 4 days from entry.
Concomitant Medications	X	X		Note: Immunosuppressive agents are recorded on a separate log page
Laboratory Tests	X			Cycle 2 and beyond: (within 72 hrs of dosing) CBC w/differential, LFTs, BUN or serum urea, creatinine. Even cycles only (within 72 hours of dosing): Fasting serum lipids profile (total cholesterol, triglycerides, LDL, and HDL), fasting glucose, and TSH (See Section 5.3).
		X		LFTS only (within 72 hours of dosing)
Pregnancy Test	X			For WOCBP Serum or urine (Note: perform q6 weeks if cycle start is delayed)
Study Samples				PK, Immunogenicity, soluble factors, miRNA, peripheral blood RNA and PBMC. See Table 5.1-5 and Table 5.1-6 for schedule of samples
Efficacy Assessments				
Tumor Assessments			X	By methods used at baseline. Tumor assessments at week 8, 16, 24, 32, 40, 48, and 56 (± 1 wk) from randomization, then every 12 wks (± 1 wk) until disease progression is documented or treatment is discontinued, whichever occurs later.

Table 5.1-2: On-Study Procedural Outline Arm A- Nivolumab (BMS-936558)				
Procedure	Each Cycle Day 1	2nd Dose of Cycle	Q 8 wks from Randomization	Notes
Clinical Drug				
Administer Study Treatment	X	X		Record study drug infusion start and stop times for nivolumab (Arm A). Doses of nivolumab should not be given less than 12 days from the previous dose. If the 2nd dose cannot be given within a 28 day window, it will be omitted and the next dose received will be Day 1 of the next cycle.
Other				
Patient-Reported Outcome Measurements	X			Prior to any study-related procedures: FKSI-DRS and EQ-5D
Health Resource Utilization	X			Except cycle 1. (Section 5.8.1)

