Table 5.1-3: On-Study Procedural Outline Arm B- Everolimus			
Procedure	Each Cycle Q 4 Weeks Day 1	Q 8 wks from Randomization	Notes
Safety Assessments			
Targeted assessments	X		Except Cycle 1. Assessments within 48 hrs of dosing to include: Targeted physical exam, performance status and weight. Oxygen saturation by pulse oximetry at rest and after exertion (Section 5.3).
Adverse Events Assessment	X		eSAEs should be approved in TAO by Investigator within 4 days from entry.
Concomitant Medications	X		Note: Immunosuppressive agents are recorded on a separate log page
Laboratory Tests	X		Cycle 2 and beyond: (within 72 hrs prior to each new cycle) CBC w/differential, LFTs, BUN or serum urea, creatinine. Even cycles only (within 72 hours prior to each new cycle): Fasting serum lipids profile (total cholesterol, triglycerides, LDL, and HDL), fasting glucose, and TSH (See Section 5.3).
Pregnancy Test	X		For WOCBP Serum or urine (Note: perform q6 weeks if cycle start is delayed)
Efficacy Assessments			
Tumor Assessments		X	By methods used at baseline. Tumor assessments at week 8, 16, 24, 32, 40, 48, and 56 (± 1 wk) from randomization, then every 12 wks (± 1 wk) until disease progression is documented or treatment is discontinued, whichever occurs later.
Clinical Drug			
Administer Study Treatment	X		First dose of study medication must be administered within 3 working days of Randomization
Study Samples			Soluble factors, miRNA, peripheral blood RNA, PBMC See Table 5.1-5 and Table 5.1-6 for schedule of samples
Other			
Patient-Reported Outcome Measurements	X		Prior to any study-related procedures: FKSI-DRS and EQ-5D
Health Resource Utilization	X		Except cycle 1. (Section 5.8.1)

Table 5.1-4: Follow-Up Assessments (CA209025) - ALL Subjects			
Procedure	X or XX, Follow-Up Visit 1+ 2^a	Y or YY, Survival Follow-Up Visits^b	Notes
Safety Assessments			
Targeted Physical Examination	X		To assess for potential late emergent study drug related issues
Adverse Events Assessment	X		All new and continuing adverse events need to be documented and followed until 100 days after last dose (X02 or XX02 visit). If drug related events continue at second follow-up visit they need to be followed to resolution or until they are deemed irreversible by the investigator. eSAEs should be approved in TAO by Investigator within 4 days from entry.
Concomitant Medications	X		

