Laboratory Tests	X		For X01 (and XX01) ONLY, repeat at X02 (and XX02) if study drug related toxicity persists. To include CBC w/ differential, LFTs, BUN, creatinine, fasting serum lipids profile (total cholesterol, triglycerides, LDL, and HDL), fasting glucose, and TSH
Pregnancy Test	X		Serum or urine
Survival Status			
Subject Status	X	X	Every 3 months (Y and YY Survival Follow-ups may be accomplished by visit or phone contact), to include subsequent anti-cancer therapy.
Efficacy Assessments			
Tumor Assessments	X	X	Only for subjects without progression on study therapy. Tumor assessments should be continued every 8 wks (\pm 1 wk) from randomization (or first dose of nivolumab for the nivolumab extension phase) for the first 12 months, then every 12 weeks (\pm 1 wk) until disease progression is documented
Study Samples Arm A Only			
PK Samples	X		See Table 5.1-5; Only for subjects ORIGINALLY randomized to Arm A, not required for nivolumab extension phase
Immunogenicity Blood Sample	X		See Table 5.1-5; Only for subjects ORIGINALLY randomized to Arm A, not required for nivolumab extension phase

Table 5.1-4: Follow-Up Assessments (CA209025) - ALL Subjects			
Other			
Patient-Reported Outcome Measurements	X	X	Collect FKSI-DRS and EQ-5D at both “X” and “XX” follow-up visits Collect EQ-5D information either in person or via telephone at “Y” and “YY” survival visits, q3 months for 1 year, then q6 months (sect. 5.3.1)
Health Resource Utilization	X		

^a X visits as follow, X1 = 30 days from last dose \pm 7 days, or may be on date of discontinuation \pm 7 days if the date of discontinuation is more than 37 days after last dose. X2 = 100-121 days from last dose (ie, 70-84 days from X1); XX01 and XX02 follow the same timeframe, but from last dose from the nivolumab extension phase

^b Y, Survival visits continue every 3 months after X visits; YY, Survival visits continue every 3 months after the XX visits (nivolumab extension phase).

Table 5.1-5: Pharmacokinetic and Immunogenicity Sampling Schedule for Subjects Originally Randomized to the Nivolumab Arm				
Study Day^a	Time (Relative to Dosing) Hour	Time (Relative to Dosing) Hour: Min	Pharmacokinetic Blood Sample Schedule	Immunogenicity Blood Sample Schedule
Day -3 to +1 (post randomization)	0 (Predose)	00:00		X
Cycle 1 Day 1	1.0 (EOI) ^b	01:00	X	
Cycle 1 Dose 2	0 (Predose)	00:00	X	X
Cycle 2 Day 1	0 (Predose)	00:00	X	
Cycle 3 Day 1	0 (Predose)	00:00		
Cycle 4 Day 1	0 (Predose)	00:00	X	X

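### No laboratory panel after screening includes sodium, potassium, calcium, magnesium, chloride or phosphate, although the dose rules act on Grade 3 or Grade 4 abnormalities of these analytes

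*Protocol*

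**What the plan says.** **Screening.** Table 5.1-1 of the protocol asks for "BUN or serum urea, creatinine, Ca, Mg, Na, K, Cl, albumin, endocrine panel" among the local tests, so calcium, magnesium, sodium, potassium and chloride are measured but phosphate is not. Table 5.1-7, for entry to the nivolumab extension phase, lists all five and adds phosphate.

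**On treatment.** For nivolumab (Table 5.1-2) the Day 1 row from cycle 2 is "CBC w/differential, LFTs, BUN or serum urea, creatinine. Even cycles only (within 72 hours of dosing): Fasting serum lipids profile", with glucose and TSH also at even cycles; the second dose of a cycle has liver tests only. For everolimus (Table 5.1-3) the row is "within 72 hrs prior to each new cycle) CBC w/differential, LFTs, BUN or serum urea, creatinine", with the same even-cycle additions. The extension-phase row (Table 5.1-8) has the same core panel, with glucose and TSH at even cycles. The on-study list in Section 5.3 agrees with the tables.

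**Follow-up.** Table 5.1-4 specifies "To include CBC w/ differential, LFTs, BUN, creatinine, fasting serum lipids profile (total cholesterol, triglycerides, LDL, and HDL), fasting glucose, and TSH" at the first follow-up visit, repeated at the second only if drug-related toxicity persists.

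**Dose rules.** Section 4.3.1.1 says nivolumab should be delayed for "Any Grade 3 drug-related laboratory abnormality, with the following exceptions for lymphopenia, leukopenia, AST, ALT, or total bilirubin". Section 4.3.4.1 says nivolumab should be discontinued for Grade 4 drug-related laboratory abnormalities, and exempts "Isolated Grade 4 electrolyte imbalances/abnormalities that are not associated with clinical sequelae" provided they are also corrected within 72 hours of onset. Section 4.3.4.2 says subjects must stop everolimus for "Any drug-related Grade 4 adverse event or laboratory abnormality, except for the following events which do not require discontinuation", and the events listed include the same electrolyte clause.

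**The concern.** The rules tell the investigator what to do about a Grade 3 or Grade 4 electrolyte or phosphate value, but after screening the schedule never produces one. A subject with symptoms will probably be tested. A subject without symptoms gives no prompt, and that is the kind of case the exemption for abnormalities without clinical sequelae has in view. Such a subject could keep receiving the drug when the protocol's own rule would delay or stop it.

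What is at stake is patient safety during dosing. In the current version this concerns subjects still on treatment and everolimus-arm subjects entering the nivolumab extension phase. Overall survival, response rate and progression-free survival are not touched.

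**Working it through.** The protocol gives no figure to reproduce. The check sets the laboratory lists beside the dose rules.

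**1. Which panels contain the six analytes (Na, K, Ca, Mg, Cl, phosphate)?**

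| Laboratory list | Analytes present |
|---|---|
| Table 5.1-1, main screening | 5 of 6 (no phosphate) |
| Table 5.1-7, extension screening | 6 of 6 |
| Table 5.1-2, nivolumab on treatment | 0 of 6 |
| Table 5.1-3, everolimus on treatment | 0 of 6 |
| Table 5.1-8, extension on treatment | 0 of 6 |
| Table 5.1-4, follow-up | 0 of 6 |
| Section 5.3, on-study list | 0 of 6 |

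**2. Which laboratory items do the dose rules name, and is each scheduled?** Sections 4.3.1.1, 4.3.4.1 and 4.3.4.2 name lymphopenia, leukopenia, neutropenia, thrombocytopenia, AST, ALT, bilirubin and electrolytes. The first four come from the blood count with differential, and the next three from the liver tests. Electrolytes are the only named class with no scheduled test after screening. Phosphate is not named in any rule; the general wording on laboratory abnormalities reaches it.

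**3. Which grades matter in each arm?** For nivolumab, Grade 3 leads to delay and Grade 4 to discontinuation unless the exemption applies. For everolimus, the specific delay triggers in Section 4.3.1.2 are pneumonitis, stomatitis and infection. There is no general laboratory trigger, so only Grade 4 values matter.

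**4. How many draws are involved?** For a subject treated for 52 weeks, 52 / 4 = 13 cycles. Cycles 2 to 13 give 12 scheduled Day 1 draws, none of which includes these analytes. Subjects treated for less time have fewer.

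**5. How often might it matter?** Among these analytes, Section 1.4.5.1 gives a nivolumab rate only for phosphate: "hypophosphatemia (1%), and lymphopenia (1%) close its list of Grade 3/4 drug-related events seen in at least 1% of the 296 subjects in CA209003. At least 1% of 296 is 2.96, so 3 or more subjects. A rate printed as 1% is below 1.5%, and 1.5% of 296 is 4.44, so at most 4.

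- 3/296 = 1.01%, exact (Clopper-Pearson) 95% limits 0.21% to 2.93%
- 4/296 = 1.35%, exact 95% limits 0.37% to 3.42%

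These are all recorded events in a study of several tumor types and doses. The share without symptoms is not given. If it is assumed to lie anywhere from 0% to 100%, the cases that symptom-led testing would miss at the observed rate run from 0 to 1.35 per 100 nivolumab subjects. This is a range under an assumption, not an estimate.

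**The case against.** The strongest reply is that nothing here is contradictory. The dose rules say what to do once an abnormality is known; they do not promise that every analyte is scheduled, and the electrolyte clause is an exemption from stopping, not a duty to look. Section 5.3 says further tests should be done as clinically indicated, and Section 6.3 requires clinically significant results to be recorded. The scheduled panel also covers every laboratory abnormality that Section 1.4.3 lists as most common on everolimus. The protocol reports no signal for sodium, potassium, calcium, magnesium or chloride, and the management guidelines in the Investigator Brochure are not available to check. All of this stands. It narrows the gap to abnormalities that no clinician had reason to test for, but does not close it.

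Three stronger readings are tempting, and the protocol does not support them:

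- **That nivolumab must be delayed or stopped.** Sections 4.3.1.1 and 4.3.4.1 say should. Only the everolimus discontinuation rule says must.
- **That the safety endpoint is under-counted.** Section 8.3.2.4 refers to specific laboratory abnormalities without naming them. Nothing shown places electrolytes among them, and such a list is commonly left to the statistical analysis plan.
- **That Section 5.3.1 contradicts Table 5.1-4.** Section 5.3.1 mentions serum chemistry at follow-up, and the only itemized list under that term, in Table 5.1-7, includes electrolytes. But Section 5.3.1 refers to Table 5.1-4 for this monitoring and does not cite the extension screening list.

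**Conclusion.** The point holds as a minor gap in safety monitoring. None of the six analytes is in any of the four post-screening tables or the Section 5.3 list, while the nivolumab delay rule and both discontinuation rules reach them. The number of missed abnormalities cannot be determined from the protocol. At the one documented rate it would be 0 to about 1.4 per 100 nivolumab subjects for phosphate, depending wholly on the unknown share without symptoms, and no rate is given for the other five.

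The scheduled gap is the same in both arms, though its consequence is narrower on everolimus, where only Grade 4 values trigger action. Because the interim result already stands as the final primary analysis, the practical benefit is to continuing and extension-phase subjects. The conclusion assumes that testing as clinically indicated is driven mainly by symptoms. If sites routinely order a full chemistry panel, fewer cases are missed, but that rests on local habit rather than on the protocol.

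**What to change.** Add sodium, potassium, calcium with albumin, magnesium, chloride and phosphate to the Day 1 local draw from cycle 2 in Tables 5.1-2, 5.1-3 and 5.1-8, and to the first follow-up draw (X01 and XX01) in Table 5.1-4. Update the on-study list in Section 5.3 to match. Albumin is needed because the corrected-calcium formula in Appendix 1 uses it, and it too is unscheduled after screening.

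The cost is amendment wording in four tables and one section, plus seven local results per cycle from draws already taken: 12 x 7 = 84 per subject treated for 52 weeks (12 x 6 = 72 without albumin). No visit is added. The downside is some incidental findings and occasional dose delays that the rules already call for. A draw every 28 days shows that an abnormality is present but does not date its onset, so it does not by itself settle the 72-hour condition.
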